3.7.1.2 Management of Cytokine Release Syndrome

CRS will be graded using the ASTCT Consensus Grading Criteria for CRS ([Table 4](#)).

Table 4 ASTCT Consensus Grading Criteria for CRS [[Lee, 2019](#)]

CRS Parameter	Grade 1	Grade 2	Grade 3	Grade 4
Fever ¹	Temperature $\geq 38^{\circ}\text{C}$	Temperature $\geq 38^{\circ}\text{C}$	Temperature $\geq 38^{\circ}\text{C}$	Temperature $\geq 38^{\circ}\text{C}$
		With		
Hypotension	None	Not requiring vasopressors	Requiring a vasopressor with or without vasopressin	Requiring multiple vasopressor (excluding vasopressin)
		And/Or²		
Hypoxia	None	Requiring low-flow nasal cannula ³ or blow-by	Requiring low-flow nasal cannula ³ , facemask, nonrebreather mask, or Venturi mask	Requiring positive pressure (e.g., CPAP, BiPAP, intubation and mechanical ventilation)

Abbreviations: ASTCT = American Society for Transplantation and Cellular Therapy; CPAP = continuous positive airway pressure; BiPAP = bilevel positive airway pressure
Organ toxicities associated with CRS may be graded according to CTCAE v5.0 but they do not influence CRS grading.

1. Fever is defined as temperature $\geq 38^{\circ}\text{C}$ not attributable to any other cause. In subjects who have CRS and receive antipyretic or anti-cytokine therapy, such as tocilizumab or steroids, fever is no longer required to grade subsequent CRS severity. In this case, CRS grading is driven by hypotension and/or hypoxia.
2. CRS grade is determined by the more severe event: hypotension or hypoxia not attributable to any other cause. For example, a patient with temperature of 39.5°C , hypotension requiring 1 vasopressor, and hypoxia requiring low-flow nasal cannula is classified as Grade 3 CRS.
3. Low-flow nasal cannula is defined as oxygen delivered at ≤ 6 L/minute. Low flow also includes blow-by oxygen delivery, sometimes used in pediatrics. High-flow nasal cannula is defined as oxygen delivered at > 6 L/minute.

General Guidance for Cytokine Release Syndrome (CRS) [Lee, 2014; Lee, 2019; BREYANZI® USPI, 2021; Porter, 2018]

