Cytokine release syndrome (CRS) is a non-antigen specific, systemic inflammatory response that occurs as result of high-level immune activation with concomitant elevations of cytokines (e.g., IL-6, IL-10, TNF- α , IL-2, interferon gamma [β IFN γ]). CRS can be fatal or have life-threatening reactions. Evaluate for and treat other causes of fever, hypoxia, and hypotension. Determine CRS grade per the ASTCT Consensus Grading criteria for CRS in [Table 4](#) and manage CRS according to this guidance or per institutional guidance. NOTE: CRS may have a similar presentation to a type 1 HSR and may be clinically indistinguishable. Ensure that 2 doses of tocilizumab are available prior to infusion of SL-172154. When tocilizumab is not available, consider using a drug with similar mechanism of action such as anti-IL-6 receptor monoclonal antibodies (e.g., sarilumab) or anti-IL-6 mAbs (e.g., siltuximab). If CRS events occur, ad hoc labs should be collected as noted in Section [6.5.9.1](#).

Severity (ASTCT CRS Consensus Grading)	Management
Any Grade	
 Permanently discontinue SL-172154 if any grade CRS occurs at Cycle 1 Day 2 or later due to ADAs against SL-172154

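### Protocol Table 4 puts low-flow nasal cannula in both the Grade 2 and the Grade 3 CRS hypoxia cells and grades high-flow cannula nowhere, so one event can fall on either side of the DLT line

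*Protocol*

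**What the plan says.** Table 4 in Protocol Section 3.7.1.2 grades CRS on fever, hypotension and hypoxia. In the hypoxia row, the Grade 2 cell begins "Requiring low-flow nasal cannula" and adds blow-by. The Grade 3 cell begins with the same words and adds "facemask, nonrebreather mask, or Venturi mask". Grade 4 is positive-pressure support.

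Footnote 3 sets low flow at ≤ 6 L/minute and states "Low flow also includes blow-by oxygen delivery, sometimes used in pediatrics". It continues: "High-flow nasal cannula is defined as oxygen delivered at > 6 L/minute". No cell of the table uses high-flow. Footnote 2 says that the more severe of hypotension and hypoxia sets the grade. Its example is a febrile patient with "hypotension requiring 1 vasopressor, and hypoxia requiring low-flow nasal cannula is classified as Grade 3 CRS".

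The general guidance below the table instructs sites: "Determine CRS grade per the ASTCT Consensus Grading criteria for CRS in" Table 4. Section 3.5 (DLT definition) and Section 9.2.4 (safety analyses) refer back to the same section for CRS grading. Under Section 3.5, an AE of Grade 3 or higher that is related or possibly related to SL-172154 and occurs in Cycle 1 of escalation is a DLT unless it is on the exception list. CRS is not on that list.

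**The concern.** One clinical picture, fever plus cannula oxygen at ≤ 6 L/minute with no vasopressor, meets two grades. A second picture, high-flow cannula alone, meets none. The overlap falls between Grade 2 and Grade 3, which is where Section 3.5 separates a non-DLT from a DLT. DLT counts drive the mTPI-2 decisions and the MTD estimate, which is a primary outcome measure.

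The grade also decides which management row applies. Grade 3 requires hospitalization, and permanent discontinuation if CRS is unresolved at 72 hours or Grade 3 recurs. The Grade 2 row has neither requirement. In expansion the DLT criteria do not apply, but the grade still affects management and the Grade 3 or 4 TEAE tables in SAP Section 8.3.

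**Working it through.** **1. The hypoxia row against its own footnote**

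| Oxygen support, no vasopressor | Grade as printed | Grade if the Grade 3 cell read high-flow |
|---|---|---|
| Cannula ≤ 6 L/minute | 2 or 3 | 2 |
| Blow-by | 2 by its own entry; footnote 3 counts it as low flow, so also 3 | 2 |
| Cannula > 6 L/minute | none stated | 3 |
| Facemask, nonrebreather or Venturi mask | 3 | 3 |
| Positive pressure | 4 | 4 |

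Footnote 3 is the main evidence of intent. Its high-flow definition has no use in the table as printed, and it groups low flow with blow-by, which is listed only under Grade 2. Footnote 2 is weaker support. Its example is Grade 3 on the vasopressor alone, so the result is the same on either reading, but it illustrates a more-severe-event rule only if low flow ranks below Grade 3. The rule itself chooses between hypotension and hypoxia, not between two grades of one hypoxia finding.

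**2. Effect of one reclassified event on the dose decision**

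Inputs from Protocol Section 9.1.1: Beta(1,1) prior, stay interval (0.25, 0.35), interval width 0.1, and a dose declared unsafe (DU) if P(rate > 0.30) ≥ 0.95. With x DLTs in n subjects the posterior is Beta(1 + x, 1 + n − x), and the interval with the highest probability per unit length decides.

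- 0/3: Beta(1,4). The density falls from zero, so the lowest interval wins: E (escalate).
- 1/3: Beta(2,3), with F(p) = 6p² − 8p³ + 3p⁴. F(0.15) = 0.1095, F(0.25) = 0.2617, F(0.35) = 0.4370 and F(0.45) = 0.6090. The masses are 0.1522 below the stay interval, 0.1753 in it and 0.1720 above it: S (stay).
- 2/3: Beta(3,2), with its mode at 2/3, above 0.35: D (de-escalate). F(0.30) = 4(0.027) − 3(0.0081) = 0.0837, so P(rate > 0.30) = 0.916 < 0.95, and it is D rather than DU.

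These agree with Table 12. The same calculation also agrees with Table 12 at n = 6 (E, E, S, D, DU for 0 to 4 DLTs) and n = 9 (E, E, E, S, D, DU for 0 to 5). Counting one low-flow event as Grade 3 instead of Grade 2 then gives:

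| n | Decision changes | Decision does not change |
|---|---|---|
| 3 | 0→1: E to S; 1→2: S to D | – |
| 6 | 1→2: E to S; 2→3: S to D | 0→1 |
| 9 | 2→3: E to S; 3→4: S to D | 0→1, 1→2 |

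From 0/3 the cost is about one further cohort of 3, because 1/6 returns to E if the next three subjects have no DLT.

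**3. How often this could arise**

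Reach of the DLT rule: about 24 of 102 planned subjects (Protocol Section 3.1.1). This is not the number expected to be affected.

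Section 1.4.7 reports no CRS to 23 April 2022, and Section 1.7.1 says the infusion reactions among the 26 monotherapy subjects were not consistent with CRS. If this is read as 0/26, the one-sided 95% upper limit is 1 − 0.05^(1/26) = 10.9%. For the 2 + 6 + 5 = 13 subjects at 3.0 or 10 mg/kg it is 1 − 0.05^(1/13) = 20.6%.

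Assumptions, not from the documents: Cycle 1 CRS in 1% to 5% of subjects, of which 10% to 25% are graded on low-flow cannula alone. The chance of at least one such event among 24 is then

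- low end: 1 − (1 − 0.01 × 0.10)^24 = 2.4%
- high end: 1 − (1 − 0.05 × 0.25)^24 = 26%

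A changed dose decision also needs the site to choose Grade 3, the event to be at least possibly related to SL-172154, and the count to be at one of the steps that changes a decision.

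**The case against.** The strongest reply is that this is one word in a table cell known here only from machine-read text, and a misread high would look just as coherent as a misprinted low. That cannot be ruled out without the PDF, and the fix depends on checking it.

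The second reply is that the table names the ASTCT criteria, the centres are described as experienced, and Section 3.7 tells investigators to err on the side of caution, so sites would grade sensibly or upward. This lowers the likelihood. But the caution sentence concerns management and assigns no grade, while the guidance sends sites to Table 4.

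Third, there are safeguards:

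- The guidelines are not prescriptive, and sites may "manage CRS according to this guidance or per institutional guidance".
- Worsening, older or comorbid Grade 2 subjects are treated as Grade 3.
- The Grade 2 and Grade 3 restart rules largely match: one dose level lower, two hospitalized infusions, at least twice the infusion time, and dexamethasone 20 mg.
- For separate organ effects, "Organ toxicities associated with CRS may be graded according to CTCAE v5.0 but they do not influence CRS grading".
- CRS attributed to ADA after Cycle 1 Day 1 leads to permanent discontinuation, itself a DLT criterion, at any grade.
- The investigator and the SMC may call other toxicities DLTs.

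Most of these soften management, not the recorded grade. The SMC provision lets DLTs be added; it does not remove a Grade 3 event that meets the definition.

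Finally, the infusion-reaction rules in Section 3.7.1.1 already assume a return to 3 mg/kg, which suggests, without proving, that dose selection is finished. If so, a memo no longer affects escalation, and the remaining value lies in re-checking recorded events and in grading from now on.

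**Conclusion.** The concern holds. As printed, Table 4 gives two grades to one CRS presentation at the DLT threshold and none to another, and nothing elsewhere in the protocol or SAP corrects it. The intended wording can be inferred from footnote 3.

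The practical size is small. CRS is expected to be rare, and the more plausible error is over-grading a low-flow event, which is conservative. Under-grading high-flow oxygen would need a literal reading that ignores footnote 3. One reclassified event can nevertheless change the dose decision at n = 3, and at some counts at n = 6 and n = 9. The 2.4% to 26% range rests entirely on the assumed CRS rates. The conclusion also assumes that the extracted cell matches the PDF. With a low likelihood, a consequence for a primary outcome measure and a very cheap correction, this should be fixed.

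**What to change.** Check the Grade 3 hypoxia cell of Table 4 against the source PDF. If the duplication is there, change low-flow to high-flow in that cell. Cannula at ≤ 6 L/minute or blow-by is then Grade 2 only, high-flow cannula or any listed mask is Grade 3, and positive pressure is Grade 4.

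Tell sites by memo and carry the change into the next amendment. Re-check the grade and, for escalation subjects, the DLT status of every CRS event recorded with oxygen support before the MTD analysis is finalized.

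The cost is one word in one cell, a memo, and a review of what should be few or no events.

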3.7.1.3 Management of Hepatotoxicity

General Guidance for Hepatotoxicity	
Severity	Management
Grade 1	
Continue SL-172154 with close monitoring.Monitor liver function at least weekly; if liver function is stable, reduce frequency of blood tests
Grade 2	
Monitor liver function approximately every 3 days. If persistent or rising liver chemistries or significant clinical symptoms, hold the next scheduled SL-172154 dose.Consider hepatology consult and liver biopsy is optional.If immune etiology is suspected, start oral prednisone 0.5 to 1 mg/kg/day (or equivalent of methylprednisolone) with 4 week taper. Resume SL-172154 at one dose level lower when toxicity \leq Grade 1 and corticosteroid taper to \leq 10 mg/day prednisone or equivalent.For Grade 2 ALT/AST increase that resolves to Grade \leq 1 within 7 days, administer next dose at same dose level.For Grade 2 ALT/AST increase that does not resolve to Grade \leq 1 within 7 days:
Hold/skip the scheduled SL-172154 dose.Resume next dose at the same dose level after ALT/AST elevations resolve to Grade \leq 1.
Grade 3	
Hold SL-172154 and monitor liver function approximately every 3 days.Grade 3 ALT/AST increase:
Hold/skip the scheduled SL-172154 dose.Resume next dose at one dose level lower after ALT/AST elevations resolve to Grade \leq 1Permanently discontinue SL-172154 for liver function test abnormality that meets following criteria in subjects who enroll with AST/ALT/total bilirubin \leq ULN: AST or ALT $>$ 8 x ULN or total bilirubin $>$ 5 x ULN for greater than 3 daysPermanently discontinue SL-172154 for liver function test abnormality that meets following criteria in subjects who enroll with AST/ALT/total bilirubin $>$ ULN: AST or ALT $>$ 8 x baseline or total bilirubin $>$ 5 x baseline for greater than 3 days.

	
 • If persistent or rising liver chemistries, or significant clinical symptoms and an immune etiology is suspected, start oral prednisone 0.5 to 1 mg/kg/day (or equivalent of methylprednisolone) with 4-week taper. Obtain hepatology consult and assessments as above, monitor liver function daily; consider liver biopsy. • After careful consultation with hepatology, consider resuming SL-172154 at one dose level lower when toxicity \leq Grade 1 and corticosteroid taper to \leq 10 mg/day prednisone or equivalent.
Grade 4	
 • Permanently discontinue SL-172154. • Consider hospitalization; obtain hepatology consult; assessments as above; monitor liver function daily; consider liver biopsy. • If an immune etiology is suspected, immediately start methylprednisolone 1 to 2 mg/kg (start with 2 mg/kg for Grade 4) or equivalent. If refractory after 3 days, consider mycophenolate mofetil (MMF). Avoid the use of infliximab in immune mediated hepatitis.

3.7.1.4 Management of Hematologic AEs

General Guidance for Hematologic Toxicity		

In the event of cytopenia, it is important to use physical exams, complete blood counts (CBCs), serum chemistries including bilirubin fractionation, D-dimer testing, and review of peripheral smears to look for evidence of RBC agglutination, microangiopathy, spherocytosis, and evidence of RBC destruction (e.g., schistocytosis, fragments). A hematologic AE needs to be distinguished from transient changes in laboratory values that can occur following SL-172154 administration (e.g., transient decrease in hemoglobin, lymphocytes, neutrophils, monocytes, platelets). The transient declines in peripheral blood counts following SL-172154 administration are thought to be due to margination of cells outside of the circulatory system in response to target engagement (especially CD40), and the cytokines released. In study SL03-OHD-101, recovery was generally observed within 24 hours. Development of persistent or progressive cytopenias should prompt evaluation of potential causes. In cases where an obvious cause cannot be identified, an autoimmune cause should be considered and investigated accordingly. No autoimmune cytopenias have been reported to date with SL-172154. In vitro studies showed binding of SL-172154 to CD47 on RBCs, however, there has been no reports of crossmatch interference to date in the clinical trials. The following are recommendations for SL-172154 dosing in the presence of anemia or thrombocytopenia in the setting of combination cytotoxic anti-cancer therapy. Investigators always have the option to perform a more conservative dose modification if clinically indicated.
		
Adverse Event	Severity	Management
Anemia	Grade 1	
 • Continue SL-172154 with close clinical follow-up and laboratory evaluation
	Grade 2	
 • Continue SL-172154 with close clinical follow-up and laboratory evaluation
	Grade 3	
 • Continue SL-172154 with close clinical follow-up and laboratory evaluation.

		
Consider if RBC transfusion is necessary to relieve anemia symptoms or to return subject to an acceptable hemoglobin (Hgb) range per institutional practice. If transfusion is required, recommend completing RBC transfusion at least 2 hours prior to the start of SL-172154 dose.Determine the etiology of anemia, consider Hematology consult.
	Grade 4	
Hold SL-172154 until AE has reverted to an acceptable hemoglobin (Hgb) range.Consider RBC transfusion to relieve anemia symptoms or to return subject to an acceptable hemoglobin (Hgb) range per institutional practice.Determine the etiology of anemia, consider Hematology consult.Discontinue SL-172154 permanently if no other etiology can be determined and SL-172154 is deemed to be the cause of anemia. Transient decrease in hemoglobin that is associated with SL-172154 infusion may not necessarily require discontinuation of SL-172154. Please consult the Medical Monitor.If anemia is not due to SL-172154, restart SL-172154 on the next scheduled dosing day at the same dose level.

General Guidance for Hematologic Toxicity (cont.)

Adverse Event	Severity	Management
Thrombocytopenia	Grade 1	
Continue SL-172154 with close clinical follow-up and laboratory evaluation
	Grade 2	
Continue SL-172154 with close clinical follow-up and laboratory evaluation
	Grade 3	
Continue SL-172154 with close clinical follow-up and laboratory evaluation. In case of recurrence where SL-172154 deemed to be the cause, reduce dose by one dose level.
	Grade 3 with bleeding or Grade 4	
Hold SL-172154 until AE is ≤ Grade 2. Restart SL-172154 on the next scheduled dosing day at one dose level lower.Consider platelet transfusion relieve thrombocytopenia symptoms or to return subject to an acceptable platelet count per institutional practice.Determine the etiology of thrombocytopenia (including chemotherapy), consider Hematology consult.At the first recurrence of Grade 3 with bleeding or Grade 4, discontinue SL-172154.

3.7.1.5 Management of Other AEs Not Specified

Severity	Dose Modification	Toxicity Management
All Grades	Note: Dose modifications are not required for AEs not deemed to be related to SL-172154 (i.e., events due to underlying disease) or for laboratory abnormalities not deemed to be clinically significant.	
• Treat accordingly, as per institutional standard
Grade 1	No dose modification required.	
• Treat accordingly, as per institutional standard
Grade 2	Consider reducing the SL-172154 by one dose level or holding SL-172154 until resolution to ≤ Grade 1 or baseline.	
• Treat accordingly, as per institutional standard
Grade 3	Hold SL-172154 until resolution to ≤ Grade 1 or baseline. For AEs that downgrade to ≤ Grade 2 within 7 days or resolve to ≤ Grade 1 or baseline within 14 days, resume SL-172154 at one dose level lower. Otherwise, discontinue SL-172154. (Note: For Grade 3 labs, decision to hold should be based on accompanying clinical signs/symptoms, the investigator's clinical judgment, and consultation with the Sponsor).	
• Treat accordingly, as per institutional standard
Grade 4	Permanently discontinue SL-172154. (Note: For Grade 4 labs, decision to discontinue should be based on accompanying clinical signs/symptoms, the investigator's clinical judgment, and consultation with the Sponsor).	
• Treat accordingly, as per institutional standard

3.7.2 Toxicity Management Guidelines for PLD

The toxicity management guidelines provided in this section represent general guidance for AEs that are considered by the investigator to be possibly related or related to treatment with PLD. Dose modifications/interruptions or delays and treatment discontinuation of PLD for toxicity management should comply with local institutional guidelines or the current regional prescribing information for management of AEs related to PLD. If the country-specific prescribing information is more conservative, the current local guidelines should be used including the special precautions for patients who reach lifetime maximums of 450 mg/m².

In the event of significant toxicity, PLD dosing may be delayed and/or dose reduced as described below. In the event of multiple toxicities, dose modification should be based on the worst toxicity observed. **Table 5** describes the dose reductions to be used for AEs that are considered by the investigator to be possibly related or related to treatment with PLD.

Table 5 PLD Dose Reduction for Management of Toxicities

Dose Level	Dose Level Reduction (mg/kg)
Starting Dose	40 mg/m ²
First Dose Reduction	30 mg/m ²
Second Dose Reduction	20 mg/m ²

3.7.2.1 Management of Hematologic Toxicity [PLD Cohort]

Neutropenia or Thrombocytopenia	PLD Dose Modification
Grade 1	
• No dose modification
Grade 2	
• Delay PLD until toxicity resolves to ANC 1.5 x 10⁹/L, platelets 75 x 10⁹/L. Resume PLD at previous dose.
Grade 3	
• Delay PLD until toxicity resolves to ANC 1.5 x 10⁹/L, platelets 75 x 10⁹/L. Resume PLD at previous dose. For prolonged or recurrent grade 3 toxicity, follow institutional standard practices.
Grade 4	
• Delay PLD until toxicity resolves to ANC 1.5 x 10⁹/L, platelets 75 x 10⁹/L. Resume PLD at one reduced dose level and consider prophylactic granulocyte growth factor support.

Abbreviation: ANC = absolute neutrophil count

3.7.2.2 Management of Infusion-Related Reaction [PLD Cohort]

Serious and sometimes life-threatening IRRs can occur with PLD. The majority of the infusion-related events occur during the first infusion. Ensure that medications to treat IRRs, and cardiopulmonary resuscitation equipment are available for immediate use prior to initiation of PLD. Administer first dose of PLD on study (C1D1) as 1 mg/min IV infusion; after Cycle 1, if tolerated, PLD can be delivered as a 1-hour infusion. Management guidelines for PLD associated IRRs are noted below.

Infusion-Related Reaction	Toxicity Management
Grade 1 or Grade 2	
Temporarily stop PLD until resolution then resume at a reduced infusion rate per local practice.Following Grade 1 or Grade 2 infusion reactions to PLD, PLD should be administered per institutional guidelines.If there is no institutional guideline, the following is recommended: 5% of the total dose should be infused slowly over the first 15 minutes. If tolerated without reaction, the infusion rate may then be doubled for the next 15 minutes. If tolerated, the infusion rate may then be completed over the next hour for a total infusion time of 90 minutes.
Grade 3 or Grade 4	
Permanently discontinue PLD

3.7.2.3 Management of Mucocutaneous Toxicity [PLD Cohort]

The following are PLD dose modification recommendations for the management of mucocutaneous toxicity, including stomatitis and palmar-plantar erythrodyesthesia (hand foot syndrome).

Severity	PLD Dose Modification
Grade 1	
If no previous Grade 3 or 4 mucocutaneous AE: Continue PLD as planned.If previous Grade 3 or 4 AE: delay PLD dose up to 2 weeks, then resume PLD at decreased dose level
Grade 2	
Delay PLD dosing up to 2 weeks or until resolved to Grade 1.If no resolution to \leq Grade 1 within 2 weeks, discontinue PLD.If resolved to \leq Grade 1 within 2 weeks, and no previous Grade 3 or 4 mucocutaneous AE: continue PLD treatment at previous dose.If resolved to \leq Grade 1 within 2 weeks but previous Grade 3 or 4 mucocutaneous AE: resume PLD treatment at decreased dose level
Grade 3	
Delay PLD dosing up to 2 weeks or until resolved to \leq Grade 1. Then resume PLD treatment at decreased dose level.Discontinue PLD if there is no resolution after 2 weeks.
Grade 4	
Delay PLD dosing up to 2 weeks or until resolved to \leq Grade 1. Then resume PLD treatment at decreased dose level.Discontinue PLD if there is no resolution after 2 weeks.

